The majority of non-hematologic AEs was mild or moderate in severity, and rates were generally similar across dosing arms with the exception of gastrointestinal events, which occurred more commonly in patients treated at 200 mg BID (39/54, 72.2%) than in patients treated at lower doses (100 mg QD: 26/52, 50.0%; 100 mg BID: 30/55, 54.5%). These events were largely grade 1 or 2 and usually occurred within the first 8 weeks on treatment. Diarrhea was common but generally manageable with standard antidiarrheal agents and tended to be short-lived: the median duration of pacritinib-related diarrhea was 2 weeks. The most common hematologic AEs were thrombocytopenia and anemia, both of which occurred more frequently in patients treated at 200 mg BID (40.7% and 24.1% respectively). Cardiac events were more common in patients treated at 200 mg BID (40.7%, n = 22) than in patients treated at lower doses (100 mg QD: 21.2%, n = 11; 100 mg BID: 21.8%, n = 12) but were largely grade 1 or 2 in severity, with the most common being peripheral edema (200 mg BID: 16.7%) and QT prolongation (200 mg BID: 7.4%). There was no excess in grade 3 or 4 cardiac events in patients treated at the highest dose (100 mg QD: 5.8%, n = 3; 100 mg BID: 5.5%, n = 3; and 200 mg BID: 3.7%, n = 2; no grade 4 events). The mean change in corrected QT interval (QTc) between Baseline and Week 24 was roughly +10 msec on all arms; no patient had a QTc > 500 msec. Bleeding events were more common in patients treated at 200 mg BID (42.6%, n = 23) than in patients treated at lower doses (100 mg QD: 36.5%, n = 19; 100 mg BID: 25.5%, n = 14) but were largely grade 1 or 2 in severity, with the most common being epistaxis (200 mg BID: 14.8%) and bruising (200 mg BID: 9.3%). There was no excess in grade 3 or 4 bleeding events in patients treated at the highest dose (100 mg QD: 7.7%, n = 4; 100 mg BID: 3.6%, n = 2; and 200 mg BID: 5.6%, n = 3; no grade 4 events). The rate of fatal events was similar across all arms: 100 mg QD: 7.7%, n = 4 (sepsis, disease progression, tuberculosis, and general state deterioration); 100 mg BID: 5.5%, n = 3 (myelofibrosis, subdural hemorrhage, and heart failure); and 200 mg BID: 5.6%, n = 3 (sepsis, respiratory failure, and subdural hematoma).

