#### **7.1.2.2 *Hematology***

Hematology parameters, (CBC, WBC, hemoglobin, hematocrit, and platelet count), will be evaluated at Screening (may be performed within 24 hours prior to the start of Screening) and daily from Days 2 through 28 or EOT, and on the day of hospital discharge. WBC differential will be evaluated at Screening (may be performed within 24 hours prior to the start of Screening), Day 8, Day 15 or EOT, Day 22, Day 28, and on the day of hospital discharge. Hematology tests are not required after hospital discharge. Analysis of CBC results will be performed at local laboratories. Results from unscheduled hematology tests should be entered into the electronic database using an Unscheduled Hematology case report form (CRF). Pacritinib/placebo dosage modifications will be implemented for clinically significant AEs identified with this testing per the guidelines for “Treatment-Related Thrombocytopenia and Bleeding” (Section 6.5.3).

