#### **8.1.4        *Serious Adverse Events***

##### **8.1.4.1        *Definition of a Serious Adverse Event***

An SAE is an AE that, at any dosage, suggests a significant hazard or side effect, regardless of its relationship to pacritinib/placebo. An AE is serious if it meets any of the criteria below:

1. Results in death
2. Is life-threatening: in the view of the investigator, the event placed the patient at immediate risk of death. This does not include an AE that, had it occurred in a more severe form, might have caused death.
3. Requires rehospitalization after discharge from the hospital or prolongation of an existing hospitalization (see Section [8.1.4.2](#))
4. Results in persistent or significant disability or incapacity or substantial disruption of the ability to conduct normal life functions
5. Is a congenital anomaly/birth defect
6. Is an important medical event that is not fatal, life threatening, or requiring hospitalization but may be considered serious if, based on appropriate medical judgment, the event jeopardized the patient and required medical or surgical intervention to prevent one of the outcomes listed above (Items 1 to 5)
7. Cancer/overdose: All cases of new cancers and drug overdose (defined as accidental or intentional ingestion of any dosage of a product that is considered both excessive and medically important) must be reported immediately using the SAE form. All cases of drug overdose, irrespective of seriousness or association with AE(s), must be reported to the Sponsor within 24 hours. Determination of seriousness will be reached in consultation with the Safety Physician, CTI BioPharma Corp. Pharmacovigilance United

States (US) Headquarters or designee. Additional instructions for reporting cancer/overdose information will be provided by the Sponsor in the study binder.

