#### **8.1.4.2      *Exceptions***

Re-hospitalizations not reported as SAEs include admissions for the following:

1. Planned, non-life-threatening medical/surgical procedures (e.g., admission for transfusion as required per local medical practice)
2. Routine health assessments requiring admission for health status documentation (e.g., routine gastroscopy, and colonoscopy)
3. Other life circumstances that have no bearing on health status and require no medical/surgical intervention (e.g., lack of housing and family circumstances)
4. Administration of study medication

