#### **Special Considerations:**

- SAEs considered to be possibly related to pacritinib/placebo or study procedure by the investigator or Sponsor shall be followed until the event resolves, stabilizes or the patient is lost to follow-up.
- SAEs assessed as unlikely related to pacritinib/placebo or study procedures shall be followed for 30 days after the last dose of pacritinib/placebo, or until the event resolves, returns to Baseline, stabilizes, or the patient is lost to follow-up, whichever comes first.
- For screened patients who are not randomized, only SAEs occurring between the time of informed consent and determination of screen failure are reported.
- All SAEs for randomized patients must have a corresponding AE recorded on the eCRF with an exact match to the event term or description.
- An SAE form should be completed for any event for which doubt exists regarding its seriousness.
- If an ongoing SAE changes in intensity, relationship to pacritinib/placebo, or as new information becomes available and/or known for the event, a follow-up SAE report

should be completed and sent to the Sponsor within 24 hours of the change in SAE assessment.

- Any SAE that occurs after treatment completion and is considered by the investigator to be related to pacritinib should be reported to the Sponsor.

A brief narrative outlining the details of the SAE and treatment and outcome is to be included on the SAE form. Follow-up information, such as laboratory reports, discharge summaries, autopsy reports, and information concerning outcome of the event, should be provided, as soon as the information becomes available and provided to CTI Pharmacovigilance via email at [contact] or [contact]).

Source documents should be submitted in English. If source documents are not in English, the investigator must summarize the source documents and provide a complete English narrative that includes a description of the event as it evolved, the results of all diagnostic procedures performed and treatments administered, and the outcome of the event.

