### **7.5.1 Adverse Events**

Summaries of adverse events will be presented by treatment arm and in total for the Safety Population.

An overview of treatment-emergent adverse events will be provided which summarizes the patient incidence of the following for the Safety Population. This overview will include the number and percentage of patients with:

- Any TEAEs,
- TEAEs related to study treatment,
- Serious TEAEs (TESAEs),
- CTCAE Grade 3+ TEAEs,
- TEAEs with outcome of death,
- TEAEs leading to study drug discontinuation, interruption, or dose reduction,
- Cardiac TEAEs (defined by MedDRA SMQ List),

- Haemorrhage TEAEs (defined by MedDRA SMQ List),

The number and percentage of patients with TEAEs will be tabulated by the highest CTCAE Grade, System Organ Class, and Preferred Term (PT).

In addition, serious TEAEs (TESAEs), CTCAE grade 3 or more TEAEs, TEAEs leading to study drug discontinuation, interruption, or dose reduction, TEAEs with an outcome of death, and related TEAEs will be summarized by System Organ Class and PT.

The PT of TEAEs of all grades and grade 3 or more TEAEs will also be presented for each treatment arm in order of decreasing frequency.

Cardiac and haemorrhage TEAEs will also be summarized by System Organ Class and PT.

For all above summaries, patients with multiple adverse events will be counted only once per System Organ Class and PT.

Listings of all AEs (i.e. including those that are not treatment-emergent), SAEs, AEs leading to treatment discontinuation, AEs leading to treatment interruption or dose reduction, AEs with outcome of death, Cardiac TEAEs, and Haemorrhage TEAEs will be provided.

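### SAE exception 1 lets a planned, non-life-threatening readmission for transfusion go unreported as serious, even when the cytopenia or bleed began or worsened on study drug

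*Protocol*

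**What the plan says.** Protocol Section 8.1.4.1, criterion 3, makes an event serious if it "Requires rehospitalization after discharge from the hospital or prolongation of an existing hospitalization", and refers the reader to Section 8.1.4.2. That section opens "Re-hospitalizations not reported as SAEs include admissions for the following", and its first item is "Planned, non-life-threatening medical/surgical procedures (e.g., admission for transfusion as required per local medical practice". It does not define what counts as planned, and it does not mention when the plan was made, whether the condition pre-dated the study, or whether study drug may be the cause.

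Other provisions that bear on the point:

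- Criterion 6 of Section 8.1.4.1 covers important medical events where "the event jeopardized the patient and required medical or surgical intervention to prevent one of the outcomes listed above".
- Section 8.1.4.3 adds: "An SAE form should be completed for any event for which doubt exists regarding its seriousness".
- Section 1.2.4, on the myelofibrosis dose-finding study PAC203, reports: "The most common hematologic AEs were thrombocytopenia and anemia, both of which occurred more frequently in patients treated at 200 mg BID". Section 6.5.2 lists anemia, thrombocytopenia and bleeding risk among the drug's known effects.
- Section 3 has discharged patients finish their course at home. Section 7.1.2.2 says: "Hematology tests are not required after hospital discharge".
- SAP Section 7.5.1 tabulates "Serious TEAEs (TESAEs") by arm. SAP Section 7.1 makes such comparisons descriptive unless stated otherwise.

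**The concern.** The printed example matches the treatment that this drug's known hematologic effects would call for. The wording suits a population with a chronic transfusion need. Most patients here enter because of COVID-19, so a transfusion admission after discharge could well reflect something new. Such an admission, if booked in advance and not life-threatening, fits the exception whatever its cause.

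What would be lost is the serious label, not the adverse event. That label drives several things:

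- reporting to the sponsor within 24 hours (Section 8.1.4.3);
- assessment for expedited reporting and the periodic SAE summaries (Section 8.1.4.4);
- the provision that important increases in serious adverse reactions are communicated to the IDMC (Section 8.4.1);
- the serious-TEAE tables in the SAP.

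The exception applies to both arms alike. Equal rules still give unequal losses if one arm has more of the exempted event, and blinding does not correct that. With no routine blood counts after discharge, a transfusion admission may also be one of the few objective signs of hematologic toxicity in an outpatient.

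**Working it through.** **Step 1. Does the exception reach a treatment-emergent case?** Take a discharged patient, still on study drug or within 30 days of the last dose, whose hemoglobin or platelets fall and who is booked for a transfusion admission.

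| Provision | Result for this patient |
|---|---|
| Criterion 3 (rehospitalization) | Met, but subject to Section 8.1.4.2 |
| Exception 1 | Applies: planned, not life-threatening, and the printed example |
| Criteria 1, 2, 4, 5 (death, immediate risk of death, disability, birth defect) | Not met in the ordinary case |
| Criterion 6 (important medical event) | Worded for events that do not require hospitalization, so read literally it does not fit; at best it turns on judgment |
| Doubt rule, Section 8.1.4.3 | Helps only if the site is in doubt; the printed example tends to remove doubt |

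The event can therefore be recorded as a non-serious AE in full compliance with the protocol.

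**Step 2. What stays serious?** An unplanned readmission for a bleed or falling counts is outside exception 1 and meets criterion 3. A life-threatening event meets criterion 2. Prolongation of the index stay is untouched, because the exceptions name re-hospitalizations only.

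**Step 3. Are the conditions known drug effects?** Yes. Section 1.2.4 gives related thrombocytopenia 25% and related anemia 25% among pacritinib-treated myelofibrosis patients. In PAC203 at 200 mg BID it gives thrombocytopenia 40.7%, anemia 24.1% and any bleeding 42.6% (largely grade 1 or 2). These figures come from a different population with a median of 21 weeks of treatment in that arm. They show which effects are known. They are not COVID-19 rates, and they are not transfusion or readmission rates.

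**Step 4. Size.** The documents state no SAE rate and no transfusion-readmission rate, so there is no plan figure to reproduce. Only the scale comes from the plan: about 200 patients, 1:1, hence about 100 per arm (Section 11.6).

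Let r_P and r_C be the proportions readmitted for transfusion on pacritinib and placebo, and f the share of them that fit exception 1 and meet no other seriousness criterion. Assume f is the same in both arms and that these patients have no other serious event. Then

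understatement of the between-arm difference = f × (r_P − r_C).

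All rates below are assumptions; results are in percentage points:

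| r_P vs r_C | f = 0 | f = 25% | f = 50% | f = 100% |
|---|---|---|---|---|
| 1% vs 0% | 0 | 0.25 | 0.5 | 1.0 |
| 3% vs 1% | 0 | 0.5 | 1.0 | 2.0 |
| 5% vs 1% | 0 | 1.0 | 2.0 | 4.0 |
| 2% vs 2% | 0 | 0 | 0 | 0 |

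For example, 50% × (3% − 1%) = 1.0 point. With 100 per arm, one point is one patient.

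**The case against.** The case on the other side is substantial, and much of it stands.

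- **The exception is narrow.** It requires a planned, non-life-threatening procedure. A reader might infer that any readmission caused by anemia, thrombocytopenia or bleeding escapes SAE reporting. The text does not support that, as step 2 shows.
- **The events remain visible as AEs.** Section 8.1.1 counts anything needing corrective or supportive therapy as an AE, and worsening of a baseline condition is also one. The SAP tabulates TEAEs by grade, grade 3 or higher, and relatedness, with a separate haemorrhage table. This stands, but it does not restore the serious label. The haemorrhage query is aimed at bleeding, not at anemia or thrombocytopenia without bleeding.
- **Detection is not wholly absent.** A planned transfusion normally implies a known blood count, and unscheduled results must be entered (Section 8.2). A CBC is due on the day of discharge, Table 3 already restricts outpatient dosing after certain thrombocytopenia and bleeding events, and outpatients are contacted weekly. This reduces the number of cases. It does not change how a case is classified.
- **PAC203 does not transfer.** Median platelets there were 55,000/µL, and hemoglobin was below 10 g/dL in 70.8%. Dosing here lasts 14 to 21 days. PAC203 showed no excess of grade 3 or 4 bleeding at the highest dose. This stands, and it is why those rates are not used to size the effect.
- **The example has a legitimate use.** The trial enrols patients with or without cancer, some of whom may have an established transfusion need. This stands: the example should be qualified, not simply deleted.

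A reader might also infer that two lost events would reach the count at which Section 8.4.1 convenes the IDMC. They would not. That trigger needs a difference above 6% as well as at least two patients. In arms of 100, above 6% means at least 7 patients, so the two-patient condition does not bind. It also counts grade 4 or 5 treatment-related AEs, so the serious label plays no part. Only the separate sentence in Section 8.4.1 on serious adverse reactions is affected.

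**Conclusion.** The gap is in the stated rule. A planned, non-life-threatening readmission to transfuse a cytopenia or bleed that began or worsened on study drug can go unreported as an SAE. Neither the important-medical-event criterion nor the doubt rule reliably recovers it.

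A reader might infer that the SAE comparison is tilted toward pacritinib. The documents support only a possible tilt. If such admissions are more frequent on pacritinib, which its known effects make plausible, the loss favours pacritinib. If they are equally frequent in both arms, or none fits the exception, the net loss is zero. The 0 to 4 point range rests entirely on assumed readmission rates and exempted shares, and the comparison concerned is descriptive. This is a reporting-definition defect worth correcting because correction is cheap. It is not evidence that the safety results would be materially wrong.

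**What to change.** Amend exception 1 of Protocol Section 8.1.4.2 and the matching SAE form instructions:

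1. Limit it to admissions scheduled before randomization, or for a pre-existing condition recorded in the medical history that has not worsened since the first dose.
2. Qualify the transfusion example in the same terms, so that routine transfusion for an established need stays exempt.
3. State that an admission for transfusion of a cytopenia or bleed that began or worsened after the first dose is assessed under criterion 3 of Section 8.1.4.1.

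This changes reporting only, not patient care. The cost is a sentence or two of protocol text, an update to the form instructions, and a few more SAE reports. The SAP's serious-TEAE tables need no change, since they follow the reported classification.

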#### **8.1.4.3      *Reporting Serious Adverse Events to the Sponsor***

SAEs, irrespective of causal relationship, will be collected during the clinical study from the time the patient provides informed consent through 30 days following the last dose of pacritinib/placebo. The site must send the paper SAE form via email ([contact]) within 24 hours of the site's first awareness of an SAE.

#### **Special Considerations:**

- SAEs considered to be possibly related to pacritinib/placebo or study procedure by the investigator or Sponsor shall be followed until the event resolves, stabilizes or the patient is lost to follow-up.
- SAEs assessed as unlikely related to pacritinib/placebo or study procedures shall be followed for 30 days after the last dose of pacritinib/placebo, or until the event resolves, returns to Baseline, stabilizes, or the patient is lost to follow-up, whichever comes first.
- For screened patients who are not randomized, only SAEs occurring between the time of informed consent and determination of screen failure are reported.
- All SAEs for randomized patients must have a corresponding AE recorded on the eCRF with an exact match to the event term or description.
- An SAE form should be completed for any event for which doubt exists regarding its seriousness.
- If an ongoing SAE changes in intensity, relationship to pacritinib/placebo, or as new information becomes available and/or known for the event, a follow-up SAE report

should be completed and sent to the Sponsor within 24 hours of the change in SAE assessment.

- Any SAE that occurs after treatment completion and is considered by the investigator to be related to pacritinib should be reported to the Sponsor.

A brief narrative outlining the details of the SAE and treatment and outcome is to be included on the SAE form. Follow-up information, such as laboratory reports, discharge summaries, autopsy reports, and information concerning outcome of the event, should be provided, as soon as the information becomes available and provided to CTI Pharmacovigilance via email at [contact] or [contact]).

Source documents should be submitted in English. If source documents are not in English, the investigator must summarize the source documents and provide a complete English narrative that includes a description of the event as it evolved, the results of all diagnostic procedures performed and treatments administered, and the outcome of the event.

#### ***8.1.4.4 Reporting Serious Adverse Events to the Regulatory Agencies, Institutional Review Boards, and/or Ethics Committees***

The Sponsor will assess SAEs for expedited reporting against the most current approved version of the Investigator Brochure. Until an AE is identified in the Reference Safety Information of the Investigator's Brochure or Summary of Product Characteristics, it is considered unexpected, regardless of whether the AE has been submitted previously as an expedited report.

Expedited reporting will be performed by the Sponsor in accordance with regulatory requirement.

Upon receiving an expedited report, the investigator must review and retain the notice with the Investigator Brochure and shall be responsible for submitting expedited reports to their Institutional Review Board (IRB)/Ethics Committee (EC) in accordance with institutional guidelines. Regardless of institutional guidelines, investigators shall submit expedited reports to their IRB/EC in the event that the Sponsor identifies an expedited report to represent a new and/or unforeseen risk.

In support of required progress reports, the Sponsor will provide the investigator and/or EC with a summary of all SAEs reported for the study at predefined intervals (e.g., quarterly) and/or upon request.

#### ***Pregnancy***

Pregnancy alone is not considered as an AE. However, if a patient becomes pregnant or causes a pregnancy during treatment and/or within 3 months of ending treatment even if the patient is withdrawn from study, this must be reported to the Sponsor immediately on the Pregnancy Reporting Form. The investigator must obtain written authorization (medical records release) from a female partner of a male patient prior to obtaining follow-up.

The investigator must follow the pregnancy either to term or termination and will collect data on both maternal and fetal outcome. All pregnancy outcomes will be recorded on the Pregnancy Reporting Form. Additional instructions for reporting pregnancy information will be provided by the Sponsor in the study binder.

Normal outcomes will be communicated to the Sponsor within 30 calendar days of birth/delivery. Abnormal pregnancy outcomes and/or any AE for the child or fetus (including miscarriage) will also be recorded in the AE eCRF and on the SAE form. The associated SAE Report Form should be sent to the Sponsor per the procedure and timelines described within Section 8.1.4.3.

### ***Overdose***

Overdose is defined as any deviation from the defined or prescribed use of pacritinib/placebo as applicable for the drug and study design. Occurrences of overdose should be reported to the Sponsor on an SAE Report Form. Reports of overdose will be evaluated on a case by case basis. Additional instructions for reporting overdose information will be provided by the Sponsor in the study binder.

